1.3.2. Study periods 1, 2, 3 and Early Withdrawal

When the following assessments are scheduled to be performed at the same time-point, the order will be as follows:

ECG > vital signs > PK and PD sampling > PainCart

Procedure	Study periods 1, 2, 3 (Days)								Early Withdrawal	Notes
	-2	-1	1	2	7	8	15	25		
Out-patient visit					X*	X	X		X	Optional in-clinic stay for participants at the discretion of investigator. *Day 7 is optional for those participants not receiving UVB.
Admission in clinical unit	X**									Optional in-clinic stay for participants at the discretion of investigator ** If subjects are not UVB-MITT participants, optional admission will be on Day-1 with Day-2 assessments completed on Day-1.
Discharge from clinical unit				X						Except if, the participant needs to remain in the Unit longer for medical reasons.
Phone Call							X			AE collection - may be out-patient visit at discretion of Investigator for additional checks
Brief Physical Examination			X	X		X	X		X	
Haematology, clinical chemistry (include liver chemistries) and urinalysis		X	X	X		X	X		X	Troponin T to be assessed on Day -1, 8, 15 (and EW if needed). C3/C4 on Day -1 only
UrDrug, BrAlc		X			X*		X			*for volunteers who do not receive UVB application, the Day 7 Assessments may be performed on Day 8 prior to PainCart
SARS-CoV-2 PCR test or rapid antigen test	X**								X	

Procedure	Study periods 1, 2, 3 (Days)								Early Withdrawal	Notes
	-2	-1	1	2	7	8	15	25		
12-lead ECG		T	X			X	X		X	Day 1: pre-dose (T), 0.5hr, 1hr post start of infusion. On other days a single measure taken prior to 1 st PainCart assessment. T = Triplicate X = Single
Vital signs (including temperature)	X**	X	X	X	X-t	X	X		X	Day 1: pre-dose, 0.5hr, 1hr, 2hr post start of infusion. X-t: temperature assessment on Day 7 for UVB-MITT population only On other days a single measure taken prior to 1 st PainCart assessment.
Randomization			X							Study period 1 only
Drug/placebo IV infusion			X							Continuous infusion over 1 hour
PainCart			X	X		X	X			Day 1 pre-dose performed twice (baseline) Day 1 performed at 1 and 3 hours post start of IV infusion. Other days performed twice ~2 hours apart at approximately the same time of day in each study period. Day 15 - heat pain detection assessment associated with UVB test performed on normal skin only. Participants not receiving UVB application will not undergo UVB heat pain detection test on irradiated skin. All other paincart assessments including heat pain detection performed on normal skin will still be assessed. See Appendix 7 for details of testing
UVB application		X			X					UVB application (2 x MED) will be performed 24hr (\pm 2hr) prior to start of infusion on Day 1. UVB application (2 x MED) on Day 7 will be performed 24hr (\pm 2hr) prior to PainCart assessment on Day 8. UVB application only applies to those in the UVB-MITT population.

Procedure	Study periods 1, 2, 3 (Days)								Early Withdrawal	Notes
	-2	-1	1	2	7	8	15	25		
AE review	X**	X	<=====→						X	
SAE review	X**	X	<=====→						X	
Concomitant medication review	X**	X	<=====→						X	
Blood samples for PK and PD			X	X		X	X		X	Day 1: pre-dose, 1hr, 3hr post-start of IV infusion. On other days samples taken prior to 1 st PainCart assessment.
Blood sample for immunogenicity			X			X			X	Day 1: pre-dose. Day 15: prior to 1 st PainCart assessment.

** If subjects are not UVB-MITT participants, optional admission will be on Day-1 with Day-2 SARS-CoV-2 test performed on Day-1.

- The timing and number of planned study assessments, including safety, pharmacokinetic, pharmacodynamic assessments may be altered during the course of the study based on newly available data to ensure appropriate monitoring.
- Any changes in the timing or addition of time points for any planned study assessments as the result of emerging pharmacokinetic/pharmacodynamic data from this study must be documented and approved by the relevant study team member and then archived in the sponsor and site study files but will not constitute a protocol amendment. The Competent Authority (CA) and ethics committee (EC) will be informed of any safety issues that constitute a substantial amendment and require alteration of the safety monitoring scheme or amendment of the informed consent form (ICF). The changes will be approved by the CA and the EC before implementation.
- The planned study assessments on Day 7 (UVB-MITT population only), 8, 15 and 25 may be performed within a ± 24hr window.
- A questionnaire related to COVID-19 is part of each visit and included in the AE review.

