1.3. Schedule of Activities (SoA)

1.3.1. Screening and follow-up

Procedure	Screening (up to 28 days before Day 1)		Follow-up check 36±4 days post last dose	Final follow-up 56±4 days post-last dose	Notes
	Part 1	Part 2			
Out-patient visit	X	X		X	Optional in-clinic stay for participants at the discretion of investigator.
Phone call			X		AE collection - may be out-patient visit at discretion of Investigator for additional checks
Informed consent	X				
Severe acute respiratory syndrome SARS-CoV-2 PCR test or rapid antigen test	X			X	
Temperature check	X	X		X	
Inclusion and exclusion criteria	X				Recheck clinical status before randomization and/or 1st dose of study intervention.
Demography	X				
Full physical examination including height and weight.	X				Weight at screening is used for determination of dose
Fitzpatrick Skin Type	X				Assessments for UVB-MITT population only Assessment to determine applying MED application
Echocardiogram	X				
Medical history (includes substance usage)	X				Substances: Drugs, Alcohol, tobacco and caffeine
Current medical conditions	X				
HIV, Hepatitis B and C	X				
Haematology, clinical chemistry (include liver chemistries) and urinalysis	X			X	Including Troponin-T (hs)
NT-proBNP	X			X	
UrDrug, BrAlc	X			X	
12-lead ECG	T			X	T = Triplicate X = Single
Vital signs	X			X	

Procedure	Screening (up to 28 days before Day 1)		Follow-up check 36 ± 4 days post last dose	Final follow-up 56 ± 4 days post-last dose	Notes
	Part 1	Part 2			
PainCart training	[X]	[X]			May be performed during either part 1 or part 2 (not both)
Minimal Erythema Dose (MED) application		X			Assessments for UVB-MITT population only. Exposure to pre-determined 6 ascending doses of UVB radiation. MED application will be the final assessment on Part 1 of Screening and will only be completed after confirmation of eligibility from available results, e.g. lab data, echocardiogram results may not be available.
MED assessment			X		Assessments for UVB-MITT population only. 24 hours (± 2 hours) after UV exposure
AE/SAE review	X	X	X	X	

- An echocardiogram performed within 3 months prior to first dosing is acceptable for enrolment into the study
- MED determination performed within 6 weeks prior to first dosing is acceptable for enrolment into the study

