2.3.1. Risk Assessment

Potential Risk of Clinical Significance	Summary of Data/Rationale for Risk	Mitigation Strategy
Investigational Product (IP)		
Hypersensitivity, including injection site and infusion reactions	
The administration of any (human) mAb has the potential to induce local or systemic immunologic reactions, for example acute allergic reactions (type I) and immune complex disease (ICD) associated with the formation of anti-drug antibodies (ADA) (type III).
 
Non-Clinical
 
In a 13-week study administration of GSK3858279 by weekly IV infusion at 100 mg/kg resulted in infusion reactions after dosing on Days 22 and 29 in one female cynomolgus monkey which was successfully managed in subsequent administrations by pre-treating with anti-histamine.
 
In the 26-week study, there were inflammatory vascular changes in multiple organs of three animals (one female at 10 mg/kg/week and one male and one female at 100 mg/kg/week) as well as mesangioproliferative glomerulopathy in the kidney of the males at 10 mg/kg/week or 100 mg/kg/week, which is consistent with ICD following the formation of ADA. Nonspecific injection site reactions caused by the subcutaneous (SC) dosing route were also noted in some monkeys, which was exacerbated by the immune complex deposition in one male. These findings were considered non-adverse.
 
Animals are not predictive for ADA-mediated adverse reactions in humans, including infusion reactions, hypersensitivity reactions or
	
Participant Selection:
 
Participants with a history of sensitivity to the study medication, or a history of any drug or other allergy that, in the opinion of the investigator, contraindicates their participation, will not be permitted to enter the study.
 
Participants with renal disorders will also be excluded.
 
Participant monitoring:
 
In Part A of FiH study (207804), participants remained in the inpatient facility for 48 hours post dosing to allow adequate monitoring by trained site personnel.
 
In Part B of FiH (207804) and in this study (209973), participants will be monitored for a minimum of two hours post dosing.
 
Emergency resuscitation facilities will also be available.
 
Participants will be instructed in the Informed Consent Form (ICF) as to the signs and symptoms of hypersensitivity reactions and be

Potential Risk of Clinical Significance	Summary of Data/Rationale for Risk	Mitigation Strategy

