3. OBJECTIVES AND ENDPOINTS

Objectives	Endpoints
Primary	Primary
To evaluate the effects of IV administration of GSK3858279 in Ultraviolet B (UVB) burn inflammatory, cold pressor test and electrical pain test in the PainCart	UVB heat pain detection (°C) Cold pressor time to intolerable pain threshold (sec) Electrical pain tolerance threshold (mA) - single stimulus
Safety	Safety
To evaluate the safety and tolerability of GSK3858279 following IV dosing	Adverse Events (AE) and Serious Adverse Events (SAE). Clinical laboratory measurements, 12-lead electrocardiograms (ECG) and vital signs that are considered of potential clinical importance.
Exploratory	Exploratory
To evaluate the PK of GSK3858279 following IV administration	Serum PK concentrations and parameters including but not limited to: area under the concentration-time curve [AUC], maximum concentration [Cmax], tmax
To evaluate the target engagement of CCL17 by GSK3858279 following IV administration	Free and total CCL17 levels in serum

Objectives	Endpoints
To evaluate the effects of IV administration of GSK3858279 in additional endpoints in UVB test, cold pressor test and electrical pain test in the PainCart	Heat pain detection on normal skin (°C) Cold pressor time to pain detection (sec) Electrical pain detection (mA) - single stimulus Electrical pain detection and tolerance threshold (mA) - repeat stimulus For each test AUC/AAC and post-test eVAS
To evaluate the effects of IV administration of GSK3858279 in pressure pain test and Conditioned modulatory pain (CPM) test in the PainCart	Pressure pain (tolerance and detection) - KPa CPM - (tolerance and detection) – mA For each test AUC/AAC and post-test eVAS
To assess the potential for anti-GSK3858279 antibody formation following IV dosing	To include: incidence, titres, and, for samples with confirmed anti-drug antibodies (ADAs), neutralising activity

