4.4. Justification for Dose and Washout Period

The dose level of 3mg/kg, the 2-week testing duration of each study period, the wash out period of at least 4 weeks, the IV route of administration and the post dose assessment times of Day 1, Day 2, Day 8 and Day 15 are selected for the PainCart study based on:

The dose by IV route is equivalent to the dose of 240mg SC proposed to be administered in an on-going repeat dose study in osteoarthritis patients (207804) and was administered in a healthy participant cohort in that study (3 mg/kg IV). Serum levels of total (complexed, free and partially complexed) GSK3858279 are below the lower limit of quantification (LLQ; 100 ng/mL) after 8 weeks following IV infusion at 3 mg/kg; based on data from a fully validated non-neutralising anti-idiotype capture (NNAIC) assay [GlaxoSmithKline Document Number [2020N429762_00](#)].

- Unbound CCL17 levels in serum have returned to approximately 30% of baseline at 4 weeks post dose.
 - A simulation plan was designed in order to investigate whether the statistical modelling for the PainCart assessments could control the potential properties of carry over effect. The plan details simulating carry over by varying different levels of drug accumulation in to the subsequent period, and the number of days it took for the drug to be eliminated. The results from the simulation showed even in the most extreme scenario (40% accumulation, 2 weeks reduction) the model was capable of extracting the treatment differences while controlling any potential carry over effects.
 - Given the statistical model chosen for analysis, and no increase in risk of safety, the washout period of at least 4 weeks is selected and still considered sufficient (data on file).
- Target engagement (percentage reduction from baseline of free CCL17) is above 90% within 24 hours of dosing IV and continues to 1-week post IV dose of 3 mg/kg. TE falls to 75% after 2 weeks post dose IV.
- t_{max} is at end of IV dose administration allowing PainCart testing to be scheduled at consistent fixed timepoints relative to dosing.

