8.8. Immunogenicity Assessments

Serum samples (approximately 5 mL) will be collected from all treated participants at pre-dose and various time points post-dosing, see SoA. Testing will be performed using the typical tiered approach involving screening, confirmation and titration assays [EMEA, 2017; FDA, 2014], performed by Clinical Immunology, GlaxoSmithKline. If sera contain potential anti-GSK3858279 antibodies, they will be confirmed by immune-competition using excess drug, followed by a titration assay. Results will include the incidence of immunogenicity, antibody specificity and titres.

For each participant, immunogenicity results, including the incidence and titres, will be reported.

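### The only participants dosed twice with GSK3858279 have no scheduled antibody sample later than about 14 days after their second active dose, although blood is drawn at the 56-day visit

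*Protocol*

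**What the plan says.** One exploratory objective in Protocol 3 reads "To assess the potential for anti-GSK3858279 antibody formation following IV dosing". Its endpoints are incidence, titre and, for confirmed positives, neutralising activity.

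Protocol 8.8 leaves the sampling times to the schedule of activities: "Serum samples (approximately 5 mL) will be collected from all treated participants at pre-dose and various time points post-dosing, see SoA". In Protocol 1.3.2 the note to the antibody row reads "Day 1: pre-dose. Day 15: prior to 1 st PainCart assessment", and the row also carries a sample at early withdrawal. The window comes from the footnote to that schedule: assessments on Day "15 and 25 may be performed within a ± 24hr window". SAP 12.2.1.2 repeats the same row.

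The screening and follow-up schedule (Protocol 1.3.1, SAP 12.2.1.1) has no antibody row for the 36-day contact or the 56±4-day visit. At the 56-day visit it does schedule "Haematology, clinical chemistry (include liver chemistries) and urinalysis", with troponin-T and NT-proBNP, so blood is drawn there.

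The protocol withholds the sequences for blinding. SAP 5.1 lists A/P/P and P/A/A only.

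For reporting, SAP 7.4.1 promises positives by treatment group and period at each assessed time, whereas the programming note for Table 2.25 presents them by period and drops the planned-time column.

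**The concern.** P/A/A is the only sequence that gives the active antibody twice, and its second active dose is also the study's last infusion. Sampling stops at Day 15 of that period, so the re-exposed participants have the shortest antibody follow-up after their latest active dose. Participants dosed once go on being sampled through two placebo periods.

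What is at stake is the reading of the antibody result. The risk table in Protocol 2.3.1 relies on sampling at baseline and at regular intervals as part of its mitigation for immunogenicity. A low incidence in the study report could be taken as reassurance about repeat dosing, when after the second dose it was observed at a single time point.

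The planned display would not show this. Without a planned-time column, a reader of Table 2.25 cannot see how long after an active dose a sample was taken. A late positive in an A/P/P participant would appear in a placebo period.

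**Working it through.** There is no planned figure to reproduce. The check is a timeline.

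**Inputs**
- Antibody samples at Day 1 pre-dose and Day 15 of each period (Protocol 1.3.2). Day 15 is 15 − 1 = 14 days after the infusion, or 13 to 15 days with the ±24-hour window.
- At least 4 weeks between doses (Protocol 1.1). At the minimum, doses fall on study days 0, 28 and 56.
- Final follow-up 56±4 days after the last dose, i.e. 52 to 60 days (Protocol 1.3.1).
- Sequences A/P/P and P/A/A (SAP 5.1).

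**Sampling times.** Pre-dose samples fall on days 0, 28 and 56, and Day 15 samples on days 14, 42 and 70. Days since an active dose = sample day − dose day, keeping positive values.

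| Sequence | Active dose | Given on day | Antibody samples, days after that dose |
|---|---|---|---|
| A/P/P | only | 0 | 14, 28, 42, 56, 70 |
| P/A/A | first | 28 | 14, 28, 42 |
| P/A/A | second | 56 | 14 |

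The P/A/A sample 42 days after the first dose is the same draw as the one 14 days after the second (70 − 28 = 42; 70 − 56 = 14). With longer dosing intervals the figures beyond 14 days in the first two rows grow. The 14 days after the second active dose does not change.

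**Unsampled time before the final visit**
- Nominal: 56 − 14 = 42 days.
- Shortest: 52 − 15 = 37 days.
- Longest: 60 − 13 = 47 days.

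**Number affected.** With equal allocation this is 30/2 = 15 of the maximum enrolled, or 24/2 = 12 of the target completers. SAP 1.1 records that the study was terminated after the futility threshold was not met, so the actual number may be smaller. The documents do not give it.

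**After the change.** A sample at the final visit would move the last observation after the second active dose from 14 days (13 to 15) to 56 days (52 to 60).

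**The case against.** The best case for leaving the plan alone has four parts.

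- **The endpoint is exploratory.** No decision rule depends on it and the PainCart analysis is unaffected. This stands, and it is why the point is minor.
- **First exposure is adequately followed.** A response started by the first active dose in P/A/A can be seen up to at least day 42, with the last of three samples taken after re-exposure. This also stands. The gap concerns the second dose only.
- **Safety is watched by other means.** Adverse events are reviewed at the 36-day contact and the 56-day visit, laboratory tests and urinalysis are done at the latter, and unexplained proteinuria or haematuria is followed up. Protocol 2.3.1 also reports a low incidence of pre-existing antibodies with low titres in Part A of the first-in-human study, and no rise with dose. So this is not a gap in clinical monitoring, though none of it measures antibodies after a second dose.
- **Later samples are possible.** Protocol 1.3.2 lets timings change on emerging data, and a participant who withdraws after Day 15 of period 3 would have a later sample. No later sample is planned for a completer.

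A reader might also infer more than the documents support:

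- **That circulating drug hides antibodies at Day 15.** Target engagement is still 75% at 2 weeks (Protocol 4.4), so drug is active then. Protocol 8.8 says of potential antibodies that "they will be confirmed by immune-competition using excess drug", which describes a reagent step in the assay. No drug tolerance is given, so any masking is unquantified.
- **That the 56-day visit is drug-free.** Protocol 4.4 says serum levels "are below the lower limit of quantification (LLQ; 100 ng/mL) after 8 weeks following IV infusion at 3 mg/kg". P/A/A receives two infusions as little as 4 weeks apart, and the visit window opens on day 52. The statement does not establish levels below quantification there.
- **That the animal data show a later onset.** Weekly dosing at 100 mg/kg "resulted in infusion reactions after dosing on Days 22 and 29 in one female cynomolgus monkey". Those days count from the start of weekly dosing, not from a last dose, and they date infusion reactions, not the appearance of antibodies. The same risk table says animals do not predict antibody-mediated reactions in humans.
- **That sampling stops before a response is due.** Neither document states an expected time to response after a first or second dose.

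**Conclusion.** The scheduling gap is real and its consequence is limited. After the second active dose, a completer's antibody status is observed once, at about 14 days (13 to 15), and the following 42 days (37 to 47) up to the final visit are unsampled. The single-dose sequence is followed to at least 70 days. The exploratory antibody objective can therefore say little about repeat dosing, and the planned table would not make that visible.

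This rests on the two sequences in SAP 5.1 and on taking the sampling day from the schedule's note, which names Day 15. The times beyond 14 days assume the 28-day minimum interval. The count of about 15 or 12 assumes equal allocation and full enrolment or completion. I rate the point as a cheap improvement of minor severity.

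**What to change.** 1. Add an antibody blood sample to the final follow-up column (56±4 days) of Protocol 1.3.1 and SAP 12.2.1.1, taken at the existing blood draw.
2. Include that time point in SAP Table 2.25 and Listing 39. Restore the planned-time column in Table 2.25, in line with SAP 7.4.1. SAP 12.6.1 runs period 3 to the final follow-up date, so without the column the new sample would merge with the earlier period 3 samples.
3. Report antibody results by sequence, with days since last active dose.
4. If final visits are already over because of the early termination, item 1 cannot be recovered. Make the changes to Table 2.25 and Listing 39 for the samples that exist, and state in the report that antibody incidence after the second active dose was observed to about 14 days only.

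**Cost.** A protocol amendment, one tube of about 5 mL and one screening assay per participant (at most 30), with no new visit or procedure. The tube is 5/500 = 1% of the 500 mL blood limit in Protocol 8. The documents do not tabulate the planned total, so the sponsor should confirm that it fits. The reporting changes need only a SAP amendment.

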2. INTRODUCTION

GSK3858279 is a high affinity, human immunoglobulin G2 σ (IgG2 σ) (Fc-silenced), first-in-class, monoclonal antibody (mAb) in development for the treatment of pain associated with osteoarthritis with a view to expand to other chronic pain diseases (e.g. neuropathic pain).

2.1. Study Rationale

The purpose of the study is to elucidate the mechanistic basis for the analgesic effects of GSK3858279 in humans by using a battery of experimental pain assessments in healthy participants. Analgesia has been demonstrated in animal models of pain with tool anti-CCL17 antibodies however the mechanistic basis for this effect seen in animal studies is not well understood and, as has been observed for other development assets, may not translate to humans. Clinical studies in pain patients can be challenging because of large placebo responses, and heterogeneity of pain mechanisms within a single disease. Performing the study in healthy participants in a controlled, validated battery of experimental pain tests assessing several pain mechanisms contrasted with historical data of analgesic drugs will inform on pain disease indications to progress.

